We hypothesize that Myrbetriq™, as a $\beta(3)$ -AR agonist⁶, could harbor a great therapeutic potential for controlling storage bladder symptoms (LUTS) and ureteral pain associated with ureteral stent placement.

Study Objective and Endpoints

The objective of this pilot study is to assess whether Myrbetriq™ will improve post-operative ureteral pain and discomfort, reduce bladder storage symptoms and increase quality of life following ureteral stenting. This study will be conducted as an exploratory pilot investigation. In doing so, we will confirm the potential effect size for reduction in associated pain following stenting within this study population. Results from this pilot study will also be used to assess feasibility for the design and conduct of a larger, prospective study in this population.

Primary Endpoints:

- Improvement from baseline in the Incontinence Symptom Severity Index (ISSI) in the Myrbetriq™ group at the 1 week follow-up and 2 week follow-up compared to placebo group.
- Improvement from baseline in the number micturition per 24 hours and the number of incontinence episodes in the Myrbetriq™ group at the 1 week follow-up and 2 week follow-up compared to placebo group.

Exploratory Endpoints:

- Improvement in pain and discomfort perception using a 10 point Visual Analog Scale for pain assessment (VAS) at the 1 and 2 week follow-up.
- Improvement from baseline on the Patient Global Impression of Severity (PGI-S) at the 2 week follow-up.

- Reduction in pain medicine intake at the 2 week follow-up.

Study Methods

This study is a prospective, randomized, double-blind, placebo-controlled 2 week clinical trial to evaluate the efficacy of Myrbetriq™ to reduce ureteral stent related pain and bladder symptoms in subjects undergoing a urologic procedure involving ureteral stenting. The study will be conducted at Southern Illinois University (SIU) School of Medicine, Department of Urology and its affiliated hospitals in Springfield, IL.

Subjects will be enrolled per the inclusion/exclusion criteria. Subjects will be screened and consented prior to their stent placement procedure for stone disease. Patients will be formally enrolled and randomized post-operatively based on no severe complications intra-operatively, such as extensive extravasation, hematoma could confound the pain and compromise the results. All subjects will complete at baseline and all follow-up visits: 1) the Incontinence Symptoms Severity Index (ISSI), 2) American Urologic Association symptom score (AUASS) 3) the Visual Analog Scale (VAS) to represent change in acute pain 4) the Patient Global Impression of Severity (PGI-S) quality of life scale 5) a voiding diary for 1 to 3 days preceding day, 7, and stent removal visits, and then 14 days after the stent removal (if done by day 28) to obtain base line diary and 6) a narcotic log starting after surgery through 14 days after stent removal (if done by day 28). The ISSI will be used to assess any change in voiding symptoms. This scale has been validated to efficiently capture and quantify urological symptoms⁷. The voiding diary is used to capture the number of micturition per day, urgency and associated incontinence. The VAS has been validated to measure changes in acute pain that are clinically significant⁸. The PGI-S has been proven to efficiently summarize a patient's perception to change in severity in regards to lower urinary tract symptoms (LUTS)⁹. Subjects will undergo a blood draw prior to stent placement (complete blood count (CBC), comprehensive metabolic panel (CMP) and urine analysis (sugar, protein, WBC/RBC, bacteria)) to verify eligibility. These laboratories will not be repeated if they were performed routinely as a part of preoperative work up. 100 subjects will be equally randomized into 1 of 2 study groups, active treatment with Myrbetriq™ or administration of a placebo. A daily 50 mg dose of Myrbetriq™ will be administered in the treatment group for up to 4 weeks initiated on the day of stent placement. A 50mg dose was chosen as the initial dose due to the acute nature of the symptoms which do not require long term therapy. It has been shown that Myrbetriq™ 50 mg taken orally once daily has superior efficacy in treatment of LUTS when compared to placebo by week 4 (the duration of this study) and this effect was maintained. A 50mg dose was proven to be safe and effective to patients in Phase III trials^{10,11}. Both study groups will receive similar prescriptions of narcotics in dose and number. Patients will be given a log to record use of narcotics. If a different form of narcotics is prescribed due to side effects or allergic reaction, a narcotic analgesia converter calculator will be used to adjust for the doses, for analysis purposes. Post-operative symptoms and pain medicine intake will be assessed at days 1, 7 via telephone interview, and with a clinic visit the day of stent removal (or day 14 if stent removal postponed) and via phone 14 days after the stent is removed. If patient is to have stent removed on day 28, or later, the patient will receive a day 21 telephone call to obtain post-operative pain and pain medicine intake, as well as questionnaires. They will remain on study drug until day 28. Use of prescription, over-the-counter and supplemental medications for pain control will be captured using self-report and direct observation/recording of medication labels by the study team. These interviews will be conducted by study staff who will be blinded to the subject's treatment. Subjects will complete

the ISSI, the AUASS, voiding diary, VAS, narcotic log, and PGI-S during these follow ups. The day 14 assessments will be collected prior to their stent removal procedure.

Study Subjects

Patients will be identified and recruited through the SIU urology clinics and St. John's Hospital during a 24 month enrollment period. Participation in this study will be completely voluntary. Male and female subjects presenting with planned stent placement for ureteral obstruction or post-ureteroscopy procedures for stone, except for those undergoing uteropelvic junction obstruction, will be evaluated for participation. Should the patient decline to participate, their choice will not change their prescribed course of standard urologic treatment. After review and approval by the local Institutional Review Board, the study will enroll 100 patients that meet the inclusion criteria below and agree to participate. Annually, the study investigators perform approximately 350 stenting procedures (based on 2 previous years of clinical data).

Inclusion Criteria

1. Age \geq 18.
2. Subject scheduled to undergo a ureteral stent placement for ureteral obstruction or post-ureteroscopy procedure.
3. Otherwise healthy subjects who are able and willing to participate in the study.
4. None of the planned interventions are documented in the labeled contraindications, warnings and precautions of the study drug.

Exclusion Criteria

1. Does NOT give consent.
2. Subject is using prohibited medications which cannot be stopped safely at the screening visit. Subject is excluded if using restricted medications not meeting protocol-specified criteria:
 - (i) Phytotherapy for BPH or a 5-alpha reductase inhibitor within 3 months, with persistent urinary symptoms and AUASS more than 7.
 - (ii) Taken an oral alpha agonist, anticholinergic or cholinergic medication within 5 days of the first screening visit with the following exception(s): a singular dose given in ER or on the hospital floor prior to procedure, topical anticholinergic eye drops used for glaucoma or inhaled anti-cholinergic used for COPD.
 - (iii) Taken tricyclic antidepressants within 2 weeks of the first screening visit.
 - (iv) Taken an estrogen, androgen, or any drug producing androgen suppression, or anabolic steroids within 3 months with the following exceptions: any topical creams for local treatment.
3. Post void residual volume $>$ 350 mL.
4. Female subject is breastfeeding, pregnant, intends to become pregnant during the study, or of childbearing potential is sexually active and not practicing a highly reliable method of birth control.
5. Subject has known neurogenic bladder.
6. Subject with uncontrolled chronic pain problems or on chronic pain medications.
7. Subject has significant stress incontinence or mixed stress/urgency incontinence where stress is the predominant factor as determined by the investigator (for female subjects confirmed by a cough provocation test).
8. Subject has an indwelling catheter or practices intermittent self-catheterization.

9. Known primary neurologic conditions such as multiple sclerosis, Parkinson's disease, diabetic neuropathy or any neurological diseases known to affect bladder function.
10. Subject has evidence of a symptomatic active urinary tract infection, chronic inflammation such as interstitial cystitis, previous pelvic radiation therapy or previous or current malignant disease of the pelvic organs, or bladder stones (which can be located in different anatomical location and can cause LUTS similar to bladder infection and pain related to their location in the bladder which could mask the treatment effect).
11. Subject who is currently under active treatment with botulinum toxin (and all other bladder paralytics) intravesically.
12. Subject has moderate to severe hepatic impairment [ALT (SGPT) or AST (SGOT) value greater than 3 times the upper limit of normal in the clinical center lab; confirmed on a second measurement].
13. Subject has severe renal impairment or End Stage Renal disease (i.e., creatinine greater than 2.0 mg/dl).
14. Subject has severe uncontrolled hypertension (defined as systolic blood pressure ≥ 180 mmHg and /or diastolic pressure ≥ 110 mmHg).
15. Subject has a clinically significant abnormal ECG in their chart or has a known history of QT prolongation or currently taking medication known to prolong the QT interval. Any patient taking Digoxin.
16. Subject has a known or suspected hypersensitivity to Mirabegron or any of the inactive ingredients.
17. Subject has a concurrent genitourinary malignancy, or active cancer (except noninvasive skin cancer) within the last 5 years prior to screening. Men with a history of prostate cancer regardless of curability are not eligible.
18. Subject has been treated with an experimental device within 30 days or received an experimental agent within the longer of 30 days or five half-lives.
19. Unable to follow protocol directions due to organic brain or psychiatric disease.
20. Intra-operative complications that require hospital admissions.
21. History of alcoholism or any other substance abuse, which, in the opinion of the investigator, would affect compliance with the protocol.

Assessment or Procedure	Baseline/ Stent Placement	Post-Op Day 1 (phone)	Post-Op Day 7 (phone)	Stent removal (Post-Op Day 14 if stent not removed) visit	Post- Op Day 21 (phone) (if stent not removed)	2 weeks after stent removal or Day 42 (phone)	Early Withdrawal
Informed Consent	X						
Verify Eligibility	X						
Review Medical & Surgical History	X						
Physical Examination (H & P)	X			BP and HR only			BP and HR only
Review Prior & Current Medications	X	X	X	X	X	X	X
Review Adverse Events		X	X	X	X	X	X
ISSI	X	X	X	X	X	X	X
VAS	X	X	X	X	X	X	X
PGI-S Quality of Life Scale	X	X	X	X	X	X	X
AUASS	X	X	X	X	X	X	X
Voiding diary			X	X		X	
Pain log		X	X	X	X	X	X
Laboratory screening tests (hematology & chemistry)	X						
Randomization	X						
Study drug administration/Accountability	X			X		X only if you have drug	X

Visit window for all visits are +/- 2 days

Study Procedures

Informed Consent

All participants will be required to provide written informed consent. The study staff will introduce the study after being informed the subject is potentially eligible. The study coordinator and/or study staff will review the informed consent document with the subject. The subject will be provided information related to the study purpose, procedures, potential risks and benefits to participation, voluntary nature of their potential participation and provide them an opportunity to ask and have answers to all questions prior to obtaining any signature. A study investigator will be available to answer any questions. Subjects will not be compensated for participation and there are no additional costs to subjects for participation in the study.

Randomization Schema

The order of group assignment will be randomized using a simple random numbers table. Equal numbers of participants will be allocated to the two study groups: Group 1: daily Myrbetriq™ (50mg) or Group 2: placebo. The randomization procedure is concealed to the participating Urologists, residents and study coordinators. The random assignment schedule will be maintained by the pharmacist at St. John's Hospital. After the patient has provided consent to participate in the study and all inclusion/exclusion criteria have been met, the study coordinator will obtain the subject's identification (ID) number.

Data Management and Confidentiality

Study coordinators will be responsible for data collection and will ensure that forms are completed and signed. Data will be entered into an excel spreadsheet for subsequent analysis. Each subject will be assigned a study identification code (ID codes). Data collection forms and consent forms will be maintained for the duration of the study in a locked file cabinet. Electronic data will be stored on a secure server accessible via password-protected computer. Only authorized study personnel will have access to the study data. Electronic data will be maintained until all analyses have been completed. Study data will be kept for six years after study completion and then destroyed.

Statistical Analyses

Due to the exploratory nature of the efficacy endpoints within this study population, we have chosen to conduct this study as a pilot clinical trial. Descriptive summary statistics will be used primarily in the exploratory efficacy analysis. Summary statistics for these endpoints will also be provided by cohort, treatment group and visit.

Data analysis will be concluded upon the completion of the study. Subjects' age, height, weight, and other continuous baseline variables will be summarized using descriptive statistics, while gender, race and other categorical variables will be provided using frequency tabulations. Medical history data will be summarized using frequency tabulations by system organ class and preferred term. Chi-square and t-tests will be used, as appropriate, to compare percent change and mean change from baseline in the ISSI, voiding diary, narcotic log, VAS score and PGI-S at the final study visit (14 days) or at any early termination visit. A split-plot ANOVA with repeated measures will be used for each measure (ISSI, VAS and PGI-S) to compare groups (Myrbetriq™ and placebo) over time and to determine if there is an interaction between groups. Significance will be assumed when $p < 0.05$. A preliminary power analysis based on previously published data, using an estimated SD for each study group of 4.17, a sample size of 50 in each study group (Myrbetriq™ and placebo) has an 80% power to detect an ISSI difference of 25% between the two groups with a significance level (alpha) of 0.05 (two-tailed)¹².

Pertinent to each Specific Aim are the following calculations:

- Primary Endpoints: Comparison of the change from baseline in ISSI and voiding diaries between Myrbetriq™ and placebo will be made using an independent t test for continuous scoring and a chi-squared test for ordinal scoring. Inferential analyses of changes from base line in micturition episodes per 24 hours and incontinence episodes per 24 hours will be performed using a stratified rank analysis to compare to baseline and as a covariance for each treatment.
- Exploratory Endpoints: Comparison of the change from baseline of total VAS between Myrbetriq™ and placebo will be made using an independent t test for continuous scoring and a chi-squared test for ordinal scoring. Comparison of the change from baseline in PGI-S between Myrbetriq™ and placebo will be made using an independent t test for

continuous scoring and a chi-squared test for ordinal scoring. Comparison of pain medicine intake between Myrbetriq™ and placebo groups will be made using an independent t test.

Safety Considerations

Screening laboratory safety tests (hematology, chemistry), blood pressure, heart rate measurements, urinalysis, and liver function tests will be performed at the initial screening visit if they are not performed as the standard pre-operative work-up. Adverse event (AE) assessments will be reviewed by the PI and reported by study personnel as Myrbetriq™ is dispensed on a daily basis. Any reported changes in patient symptoms will be reviewed again at the end of the study. AEs will be summarized by treatment group according to the last treatment taken before the AE took place.

Data Safety Monitoring Plan

The investigators will be responsible for all study assessments and will monitor each participating subject for any adverse events. An adverse event log has been created for this study and side effects of study subjects will be collected, tabulated and reviewed. Regularly scheduled meetings of study personnel will take place (at least monthly) to review study progress and procedures. Real time management of AEs will be done per standard of care by the subjects' health care providers. Any serious AE or unanticipated problems will be reported to the Springfield Committee for Research Involving Human Subjects (SCRIHS) within 24 hours in accordance with SCRIHS policy.

Institution and Investigator Interests

SIU School of Medicine and the Principal Investigator, [name] received a grant from Astellas to support the costs of conducting this clinical trial. Astellas is the manufacturer of the drug (Mirabegron) being used in this study. Astellas is also providing the drug free of charge to subjects while participating in this study.

References

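### The protocol promises a pain effect size, but the analysis plan prespecifies no between-group VAS estimate or confidence interval, and its t test on change is less efficient than baseline adjustment

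*Combined protocol and SAP*

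**What the plan says.** Under Study Objective and Endpoints, the combined protocol and SAP sets a three-part objective: to "assess whether Myrbetriq™ will improve post-operative ureteral pain and discomfort, reduce bladder storage symptoms and increase quality of life following ureteral stenting". It then adds that "we will confirm the potential effect size for reduction in associated pain following stenting within this study population". It also says that "Results from this pilot study will also be used to assess feasibility for the design and conduct of a larger, prospective study".

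Pain is an exploratory endpoint: "Improvement in pain and discomfort perception using a 10 point Visual Analog Scale for pain assessment (VAS) at the 1 and 2 week follow-up".

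Statistical Analyses handles VAS in four ways:

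- Descriptive summaries are the main exploratory efficacy output, presented by cohort, treatment group and visit. The statistics to be summarised are not listed.
- A general sentence applies chi-squared and t tests to percent change and mean change in several measures, including VAS, at the final 14-day visit or at early termination.
- A split-plot repeated-measures ANOVA compares the groups over time on ISSI, VAS and PGI-S.
- The exploratory-endpoint bullet reads: "Comparison of the change from baseline of total VAS between Myrbetriq™ and placebo will be made using an independent t test for continuous scoring", with a chi-squared test for ordinal scoring.

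The decision rule is "Significance will be assumed when" p < 0.05. The only power statement concerns ISSI. No confidence interval is mentioned for any endpoint.

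**The concern.** A pilot that is meant to supply an effect size should say in advance which number that is and how precisely it will be known. This plan leaves several candidates open: mean or percent change, continuous or ordinal scoring, and weeks 1 and 2 (endpoint list) or the 14-day visit (general test sentence). The ANOVA does not say which visits enter, although the schedule also collects VAS at day 1, at day 21 if the stent is still in, and two weeks after removal. The planning figure could therefore be chosen after the data are seen, and might be carried into the next trial's sample size with no statement of its uncertainty.

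There is also a loss of efficiency. Baseline VAS is scheduled for every subject, but a t test on change subtracts it with a fixed weight of one. Regression adjustment estimates that weight and gives a narrower interval from the same data.

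**Working it through.** **Inputs from the documents.** 100 subjects randomised 1:1, so 50 per arm; two-sided alpha 0.05; SD 4.17 and 80% power for a 25% difference in ISSI. **Not in the documents, so assumed:** VAS SD (2 to 3 points on the 10-point scale), baseline to follow-up correlation r (0.3 to 0.5), and the number evaluable.

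**1. The plan's own figure.** With 50 per arm and SD 4.17, the difference detectable with 80% power is (1.960 + 0.842) × 4.17 × √(2/50) = 2.34 points (2.36 using the t distribution). For this to be 25% of a reference mean, that mean would have to be about 9.3 to 9.4. The documents do not give it, so the 80% cannot be fully reproduced. The figure concerns ISSI in any case; VAS has no corresponding statement.

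**2. Precision of an unadjusted VAS difference.** Half-width of the 95% interval = t(0.975, 98) × SD × √(2/50) = 1.984 × 0.2 × SD = 0.397 SD, where SD is that of the variable being compared.

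- SD 2: 0.79 points
- SD 2.5: 0.99 points
- SD 3: 1.19 points

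With 40 evaluable per arm (assumed) the half-width is 0.445 SD, or 0.89 to 1.34 points for SD 2 to 3.

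**3. What an interval would show.** The standard error of a standardised difference d is √(2/50 + d²/200). An observed d of 0.5 has a 95% interval of 0.10 to 0.90; an observed d of 0.3, −0.09 to 0.69. Power at 50 per arm is about 70% for a true d of 0.5 and 32% for 0.3, so a non-significant test would say little about the size of the effect. The pooled SD, on 98 degrees of freedom, would have a 95% interval of 0.88 to 1.16 times its estimate, which is usable for planning.

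**4. Change score against ANCOVA.** Let σ be the VAS SD at a visit, taken as equal at baseline and follow-up.

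- Variance of change: 2σ²(1 − r)
- ANCOVA residual variance: σ²(1 − r²)
- Ratio: (1 − r²) / [2(1 − r)] = (1 + r)/2

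| Assumed r | Variance ratio | Half-width, change score | Half-width, ANCOVA |
|---|---|---|---|
| 0.3 | 0.65 | 0.397 × √1.40 = 0.47σ | 0.397 × √0.91 = 0.38σ |
| 0.5 | 0.75 | 0.397 × √1.00 = 0.40σ | 0.397 × √0.75 = 0.34σ |

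For σ of 2 to 3 points, the half-width falls from 0.94–1.41 to 0.76–1.14 points at r = 0.3, and from 0.79–1.19 to 0.69–1.03 points at r = 0.5. The one degree of freedom spent on the covariate is ignored. To match ANCOVA at 50 per arm, the change-score analysis would need 50/0.65 = 77 or 50/0.75 = 67 per arm.

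**The case against.** The best defence is that descriptive statistics, not tests, are the stated main output for exploratory efficacy. If the summaries by group and visit report means and SDs, as is usual, a reader can derive the VAS difference, pooled SD and standardised effect by arithmetic. That stands. A reader might infer that VAS will yield nothing but a p-value, or that no SD is planned; the documents do not support either inference. What the summaries leave open is which derived figure is the effect size, and its interval.

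It can also be said that a t test on change is valid under randomisation. It is. The case for ANCOVA is efficiency, not bias.

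Finally, the width of the interval follows largely from 50 per arm, and reporting it does not narrow it. That is right for the unadjusted interval; the adjustment is what narrows it.

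A reader might also suppose that baseline VAS is taken before stenting, so that change mixes relief of the presenting pain with stent pain. The documents do not settle the timing: the schedule's baseline and stent-placement column also contains randomisation, which Study Methods places after the operation. Even with a pre-stent baseline, such relief would be expected in both randomised arms and would not bias the contrast between them.

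**Conclusion.** The point holds as a gap in prespecification together with a free gain in efficiency. The pain effect size is one of several stated purposes, and for that purpose the plan names neither the between-group estimate nor its interval. On the assumed SDs the unadjusted half-width is 0.8 to 1.2 points. Against change scores, ANCOVA lowers the variance by 35% at r = 0.3 and 25% at r = 0.5. These sizes rest on assumed SDs and correlations, equal variances at the two times, complete follow-up at 50 per arm, and a baseline VAS recorded before the first study dose.

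Two stronger conclusions are not supported. One is that the trial cannot confirm a pain effect: that depends on the true effect and on an important difference, and the documents give neither. The other is that the sample size is wrong: it was set on ISSI, and nothing here bears on it. *Estimate* is the better word because it describes what an exploratory pilot with an exploratory pain endpoint is set up to do.

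**What to change.** - **Statistical Analyses, Exploratory Endpoints:** replace the t test on VAS change with ANCOVA of follow-up VAS on treatment and baseline VAS, at week 1 and at week 2. State which scheduled assessment counts as week 2.
- In the same place, name the adjusted mean difference (Myrbetriq minus placebo) with its 95% confidence interval, together with the SD, as the pain effect size. Bring the general sentence on t and chi-squared tests into line for VAS.
- **Study Objective and Endpoints:** change *confirm* to *estimate* in the sentence on the pain effect size.

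The cost is wording only. No visit, measurement, patient or change in endpoint hierarchy is needed, because baseline and follow-up VAS are already scheduled. The objective becomes slightly more modest.

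### The diary primary endpoint is a change from baseline, but no diary is scheduled before randomisation and the one called baseline is kept 14 days after stent removal

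*Combined protocol and SAP*

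**What the plan says.** All references are to the combined protocol and SAP.

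- **Study Objective and Endpoints, Primary Endpoints:** "Improvement from baseline in the number micturition per 24 hours and the number of incontinence episodes", at the 1-week and 2-week follow-ups, active against placebo.
- **Study Methods, order of events:** "Subjects will be screened and consented prior to their stent placement procedure"; then "Patients will be formally enrolled and randomized post-operatively". Study drug starts on the day of stent placement.
- **Study Methods, list of instruments:** the list opens with "All subjects will complete at baseline and all follow-up visits". Its voiding-diary item then gives its own times: 1 to 3 days before the day-7 and stent-removal visits, "and then 14 days after the stent removal (if done by day 28) to obtain base line diary".
- **Study Methods, end:** patients complete "the ISSI, the AUASS, voiding diary, VAS, narcotic log, and PGI-S during these follow ups".
- **Schedule of assessments:** the diary is marked at Day 7, at stent removal (or Day 14 if the stent stays in), and at the last phone contact, which is two weeks after removal or Day 42. It is blank at Baseline, Day 1, Day 21 and Early Withdrawal. ISSI, VAS, PGI-S and AUASS are all marked at Baseline.
- **Statistical Analyses:** "Comparison of the change from baseline in ISSI and voiding diaries between" the arms is by t test or chi-squared test. Changes in the two diary counts also get a "stratified rank analysis to compare to baseline and as a covariance for each treatment". An earlier paragraph of that section takes the diary change at 14 days or at an early termination visit.

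**The concern.** A change from baseline normally subtracts a value that treatment cannot have touched. Here the only diary labelled as baseline comes after randomisation, after the start of study drug and after the stent is out. Two things then matter for the comparison of arms.

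- If some treatment effect were still present at the late diary, subtracting it or adjusting for it would remove part of the effect being estimated.
- If having a late diary depends on events after randomisation, such as late stent removal or withdrawal, the patients with a change score are no longer all those randomised.

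The trial is a pilot with mainly descriptive analysis. However, this endpoint is listed as primary, inferential tests are planned for it, and the results are meant to inform a larger study.

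**Working it through.** **1. Is there a pre-randomisation diary?** The lead-in to the instrument list mentions baseline, but it covers six instruments at once. The diary item under it sets specific times, none before surgery. The schedule agrees with the item: its diary row is empty at Baseline and Day 1. The phrase giving the first diary time may have lost a number, but those empty cells leave no place for an earlier diary. The sentence about follow-ups at the end of Study Methods neither adds nor rules out a baseline diary.

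**2. What would the analysis use?** Statistical Analyses does not say which diary is its baseline. The only one so named is the post-removal diary, so both the change score and the covariate would rest on it.

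**3. Is that diary unaffected by treatment?** Treatment lasts up to 4 weeks. Continuing drug to day 28 is stated only for patients whose stent comes out on day 28 or later. For earlier removals, drug status at the last contact is not stated. The text leans towards off drug, but the accountability row of the schedule allows for drug still being held then.

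**4. Is it available for everyone?** Study Methods makes it conditional on day 28; the schedule allows two weeks after removal or Day 42. Day 42 may be a cap (28 + 14 = 42), but this is not said. Read literally, Study Methods leaves late removals without a reference value. At early withdrawal the analysis expects a diary that the schedule does not mark. No missing-data rule is given.

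**5. Size, as an illustration only.** The plan's one power figure, 80% with 50 per group, is for ISSI. No diary SD, effect or power is given, so every input here except the 50 per arm and the two-sided alpha of 0.05 is an assumption.

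The effect is set at d = 0.566 SD, which gives 80.0% power for an unadjusted t test with n = 50 per arm. Both diaries have equal SDs. Power comes from the noncentral t distribution with noncentrality λ = effect / (residual SD × √(2/n)); √(2/50) = 0.200 and √(2/40) = 0.2236.

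*No effect left at the late diary.* Residual SD is √(1 − q²) for the direct comparison, where q is the correlation of the diary with the baseline score (0.2 to 0.5). It is √(1 − ρ²) with the late diary as covariate, where ρ is the correlation of the two diaries (0.3 to 0.7). Degrees of freedom are 2n − 3. For example, at q = 0.2 and n = 50, λ = 0.566 / (0.980 × 0.200) = 2.89, giving 81.6%.

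| Analysis | 50 per arm | 40 per arm (20% missing) |
|---|---|---|
| Direct, adjusted, q = 0.2 to 0.5 | 81.6% to 89.9% | 72.3% to 82.3% |
| Late-diary covariate, ρ = 0.3 to 0.7 | 83.6% to 97.5% | 74.5% to 93.8% |

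*A share k of the effect left at the late diary, ρ = 0.5, n = 50.*

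- The change score has effect d(1 − k) and SD √(2 − 2ρ) = 1. Power is 80.0% at k = 0, 55.6% at k = 0.25 and 29% at k = 0.5.
- The covariate analysis has effect d(1 − ρk) and SD √(1 − ρ²) = 0.866, with a variance factor of 1 + (kd)²/4. Power is 89.9%, 80.6% and 67.1%.
- The direct comparison does not depend on k.

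**The case against.** The best defence is that a stent-free reference is a deliberate and reasonable choice. The endpoint is a comparison with placebo. If nothing carries over and the late diaries are complete, the between-arm difference in change has the same expectation whichever stent-free diary is subtracted. That stands, and it limits the point in three places where a reader might infer more.

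- *That the endpoint cannot be computed.* It can, wherever the late diary exists: the endpoint says baseline, and Study Methods says which diary supplies it.
- *That measuring excess over a stent-free state is peculiar to the late diary.* It is not. A pre-operative diary would generally be free of the study stent too. What sets the late diary apart is that it follows randomisation.
- *That the estimate is biased towards zero.* The documents do not show this. They lean towards patients being off drug, the drug-held entry may only concern returned supply, and nothing supports any particular k above zero.

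It is also fair that the power figures use t tests and linear covariance while the plan names a rank analysis, and that missing diaries would affect any analysis. The table above therefore applies 20% to both methods. Finally, the ISSI validation paper in the reference list concerns women while the trial enrols both sexes, so the gain from adjustment may be small.

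None of this supplies a pre-randomisation diary or settles drug status and availability at the late one.

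**Conclusion.** The point holds as a gap between definition and schedule. A primary endpoint described as improvement from baseline would be analysed against a post-randomisation value whose independence from treatment, and whose completeness, the documents do not secure. The consequence is a risk of bias and of lost patients. Its size cannot be estimated from the documents, which give no late-removal rate, withdrawal rate or diary SD. If no effect persists and availability is unrelated to treatment, the arm comparison is valid.

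The defect is confined to the diary endpoint. ISSI, the only endpoint with a power statement, has a true baseline. In a mainly descriptive pilot this should be fixed, but it does not undermine the trial as a whole. Confidence is high that no pre-randomisation diary is scheduled, and lower about the consequences.

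**What to change.** 1. Make the primary diary analysis a direct between-arm comparison of the day-7 and stent-removal/day-14 counts, in all randomised patients with a diary at that visit, adjusted for baseline ISSI and AUASS. The rank method can stay, with these scores as covariates in place of the late diary.
2. Reword the diary endpoint under Primary Endpoints to match.
3. Keep change from the post-removal diary as a labelled stent-free reference or a sensitivity analysis.
4. Reconcile Study Methods, the schedule and Statistical Analyses on when the late diary is due, on drug status at that contact, and on whether a diary is collected at early withdrawal. No clinical rule is proposed here.

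**Cost.** Wording only: no new visit, form or patient. The endpoint stops being a change score, and some precision may be lost if no effect persists at the late diary (the illustrative ranges are in the table above). Two limits remain: on-stent diaries can also be missing, and the date of the second one still depends on when the stent is removed.

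A pre-operative diary would keep the written endpoint, since patients consent before surgery. It would add a form, however, and could not be obtained for anyone already randomised.
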